### **5.5 Evaluation of Maternal Perspectives:**

All interviews will be audio-recorded.

Questionnaires will include questions pertaining to the following topics:

- How well-prepared for the intervention mothers felt
- Whether they felt staff gave good explanations during the intervention
- Whether they understood the interventions taking place
- Whether they felt the intervention was traumatic or stressful, increased worry, provided reassurance
- Whether they would want to be in close proximity again should they be presented with a similar situation

Interview questions will address the following topics:

- How the experience in the delivery room could have been improved
- If there are things that could have been explained ahead of time that would have resulted in an improved experience
- How parents felt while their babies were being intubated
- The impact of having additional providers in the delivery room

## **STATISTICAL CONSIDERATIONS**

### **5.6 Primary Endpoint**

The primary endpoint will be successful completion of the DING intervention for those subjects allocated to the interventional arm of the study. Infants who are intubated and have ventilation initiated prior to UCC and prior to 3 minutes of life will be considered to have successfully completed the protocol

### **5.7 Secondary Endpoints**

Secondary endpoints include arterial pH and PaO2 on first blood gas, oxygenation index [OI] throughout first 24 hours of life [HOL], need for vasopressors (first 24 HOL), presence of severe pulmonary hypertension on first echocardiogram, need for ECMO and mortality during hospitalization for both the subject allocated to the interventional arm and the historical controls.

### **5.8 Tertiary Endpoints:**

Identification of salient themes in parent experiences of the DING intervention, Identification of factors during the intervention that mothers identify as stress inducing or alleviating.

---

## **5.9 Statistical Methods**

### **5.9.1 Baseline Data**

Baseline characteristics, the primary, secondary, and tertiary endpoints, and safety evaluations will be summarized by standard descriptive summaries.

### **5.9.2 Primary Analysis**

The primary analysis will be based on an intention to treat approach. All infants who meet all eligibility criteria at the time of birth and are allocated to the intervention are considered evaluable. The proportion of evaluable infants who successfully complete the DING intervention will be reported as the primary outcome.

### **5.9.3 Secondary Outcomes**

We will compare secondary clinical outcomes between evaluable DING participants and evaluable historical controls who are enrolled in the Pulmonary Hypoplasia Program (PHP) registry ([IRB#06-003779](#)).

Controls will be identified from the CHOP Pulmonary Hypoplasia Program registry, which contains detailed information about infants with CDH treated at CHOP. For each DING participant, we will select the most recent historical control, matched for gestational age and CDH severity markers. Matched historical controls will be considered evaluable if they meet all inclusion and exclusion criteria and their medical record is complete for comparison.

We will ascertain the specified secondary clinical outcomes for control infants. The data for the controls will come from the PHP registry (IRB # 3799).

We will compare the short-term outcomes between groups, using Student's t test or Wilcoxon rank sum test for continuous variables and chi square or Fisher's exact test for dichotomous variables.

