#### **4.2.2 Matched Historical Controls**

Medical record review will include the specified secondary clinical outcomes for control infants.

---

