## 5.2 Screening and Monitoring Evaluations

### 5.2.1 Medical Record Review – for both interventional arm and historical controls

We will abstract the following variables from the maternal and infant chart:

- Baseline characteristics
    - Prenatal ultrasound findings
    - Gestational age at prenatal diagnosis
    - Date of birth
    - Time of birth
    - Mode of delivery
    - Gestational age
    - Birth weight
    - Sex
    - Race
    - Ethnicity
  - Type and timing of resuscitation interventions in the delivery suite and SDU:
    - Intubation
      - Number of attempts
      - Time of successful intubation
      - Tracheal intubated adverse events, using NEAR4Neos operational definitions
    - Interval between birth and UCC (for interventional arm only)
    - Chest compressions performed
    - Medications and fluids administered
    - Supplemental FiO2
    - Ventilator settings
    - Vital signs during resuscitation (temperature, heart rate, respiratory rate, blood pressure, pulse oximetry)
  - Cardiorespiratory Interventions and diagnostic tests in first 7 days of life
    - Vital signs (heart rate, pulse oximetry, blood pressure)
    - Supplemental FiO2
    - Ventilator settings
    - Vasopressors (type and dose)
    - Laboratory tests (blood gasses, complete blood count, bilirubin level)
    - Echocardiogram findings
  - Clinical outcomes during hospitalization
    - ECMO cannulation (occurrence and day of life)
    - Mortality (occurrence, day of life, and cause)
  - Maternal chart review (outcomes will be ascertained in first 7 days after delivery, or until discharge- whichever period is shorter – for interventional arm only)
    - Estimated blood loss at delivery (all deliveries)
    - Need for therapeutic uterotonics (all deliveries)
    - First post-partum hemoglobin (all deliveries)
-

- OR time (for Cesarean deliveries)
- Contamination of sterile field (for Cesarean deliveries)
- Surgical wound infection (for Cesarean deliveries)

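### Historical controls must pass an undefined record-completeness test that DING infants do not face, so a control with known death and ECMO status could be dropped because other data are missing

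*Combined protocol and SAP*

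**What the plan says.** All references are to the combined protocol and SAP.

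- **Controls.** Section 5.9.3 (Secondary Outcomes): "Matched historical controls will be considered evaluable if they meet all inclusion and exclusion criteria and their medical record is complete for comparison". No section says which items must be present, who judges this, or when.
- **DING infants.** Section 5.9.2 (Primary Analysis): "All infants who meet all eligibility criteria at the time of birth and are allocated to the intervention are considered evaluable". No other definition of an evaluable DING infant is given.
- **Comparison.** Section 5.9.3: "We will compare secondary clinical outcomes between evaluable DING participants and evaluable historical controls". The tests are unpaired: Student's t test or "Wilcoxon rank sum test for continuous variables and chi square" or Fisher's exact test for binary outcomes.
- **Endpoints.** Section 5.7 lists, for both groups, first-gas pH and PaO2, oxygenation index (OI) over 24 hours, vasopressor use, severe pulmonary hypertension on the first echocardiogram, ECMO and in-hospital death.
- **Data sources.** Section 4.2.2 says: "Medical record review will include the specified secondary clinical outcomes for control infants". Section 5.2.1, headed as applying "for both interventional arm and historical controls", includes ECMO and mortality among the items to abstract. Section 5.9.3 also names the Pulmonary Hypoplasia Program (PHP) registry as the source of control data. Section 5.2.3 says that laboratory values come from routine care, with none obtained for the study.

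The document has no rule for missing outcome data and does not say whether a rejected control is replaced.

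**The concern.** The completeness condition acts on one group only. Control records already contain their outcomes when completeness is judged, the criterion is open, and nothing requires the control list to be settled before outcomes are read. If infants whose records are incomplete differ in outcome from the rest, the retained controls no longer represent the eligible, matched infants from whom they were drawn.

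Death and ECMO are the endpoints most exposed, because they can be known even when a blood gas, an OI value or an echocardiogram is not. What is at stake is the secondary comparison and its later use: section 5.10 intends the secondary outcomes to inform power calculations for a randomised trial and makes estimation the analytic aim.

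**Working it through.** **Step 1: the two rules side by side.**

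| | DING infants (5.9.2) | Historical controls (5.9.3) |
|---|---|---|
| Eligibility criteria met | required | required |
| Other entry condition | allocated to DING | matched to a DING infant |
| Record complete | no condition | required, undefined |
| Unit to which the rule applies | infant | infant |

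This assumes that the word evaluable keeps its 5.9.2 meaning for DING infants when 5.9.3 uses it again. Since no other definition exists, that is the natural reading.

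**Step 2: which endpoints are exposed.** For a blood gas, OI or echocardiogram endpoint taken alone, an infant without a value drops out of that test in either group. The asymmetry appears when a gap on one endpoint removes a control from another endpoint on which its status is known. Because the tests are unpaired, the matched DING infant stays in when its control goes.

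**Step 3: possible size.** The plan gives no figure for the share of records rejected, so there is none to reproduce. Its only relevant counts are 20 DING + 20 controls = 40 (section 3.3.2). For illustration, let p be the true control event rate, f the share of records rejected among infants with the event, and g the share among those without. Then

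retained rate = p(1−f) / [p(1−f) + (1−p)(1−g)].

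The values of p are the background CDH rates in section 1.1 (ECMO 33%, death 29%), which are not rates for this eligible population. Every f and g is an assumption.

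| Outcome | f | g | Calculation | Retained rate |
|---|---|---|---|---|
| ECMO | 10% | 0 | 0.297 / 0.967 | 30.7% |
| ECMO | 25% | 0 | 0.2475 / 0.9175 | 27.0% |
| ECMO | 10% | 10% | equal rejection | 33.0% |
| ECMO | 10% | 15% | 0.297 / 0.8665 | 34.3% |
| ECMO | 0 | 25% | 0.33 / 0.8325 | 39.6% |
| Death | 10% | 0 | 0.261 / 0.971 | 26.9% |
| Death | 10% | 10% | equal rejection | 29.0% |
| Death | 10% | 15% | 0.261 / 0.8645 | 30.2% |
| Death | 0 | 25% | 0.29 / 0.8225 | 35.3% |

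The sign depends on whether f exceeds g, and equal rejection gives no bias. Replacing rejected controls with others that pass the same filter leaves the expected rate where the formula puts it.

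**Step 4: in counts.** Suppose 6 of 20 controls died (30.0%). If one, two or three of those deaths were dropped for other missing data, with no replacement, the rate becomes 5/19 = 26.3%, 4/18 = 22.2% or 3/17 = 17.6%. This is a deliberately extreme case, since every dropped control is a death.

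**Step 5: against sampling error.** For ECMO in 7 of 20 controls (35%, the nearest whole count to 33%), the exact 95% confidence interval is 15.4% to 59.2%. The shifts in Step 3 run from 0 to 6.6 points, well inside it.

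**The case against.** The strongest reply is that the phrase can equally mean complete for the comparison in hand. On that reading, a control with known vital and ECMO status stays in those comparisons. Sections 5.2.1 and 5.7, which abstract ECMO and death and list them as endpoints for both groups, fit that intention. This stands: the harmful reading is permitted by the text but not required by it.

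A reader might go further and infer that controls who died or went on ECMO will be lost, which would make DING look worse. The documents do not support that. They do not say that early death or ECMO leaves gaps. The first gas and first echocardiogram are early single measurements, OI may be complete up to death, and section 5.9.3 describes the registry as detailed. The link between outcome and completeness is an inference, and the opposite pattern would shift the rates the other way.

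Nor can one infer that gaps are equally likely in both groups. Control data are attributed both to medical record review and to the registry, so common sourcing is not established.

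Two further replies have partial force. Section 5.9.3 already selects the most recent matched control with no outcome criterion, but the completeness condition comes on top of that selection. Removing the condition altogether would lose a legitimate check, because a control without eligibility or matching data cannot be used; the remedy should therefore narrow it. Finally, section 5.10 does not expect significant differences, but estimation is its stated aim, and a confidence interval does not reveal selection bias.

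**Conclusion.** The point holds as a minor one. The plan applies an undefined completeness condition to controls only, sets evaluability per infant, and has no missing-data rule. Together these permit a control with known death and ECMO status to be excluded when a DING infant with the same gap would be counted.

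Bias follows only if completeness is related to outcome, which the documents neither state nor rule out. Its direction and size are unknown. The illustrative shifts rest on assumed rejection shares and background event rates, and they are small beside the uncertainty of 20 controls. The primary endpoint has no control group and the safety analysis covers only allocated DING infants, so neither is affected.

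**What to change.** In section 5.9.3:

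1. Limit the completeness condition to the variables needed to establish eligibility and to match.
2. Select the most recent matching control without reference to outcomes, and fix the list before any outcome is abstracted.
3. Count death and ECMO for every selected control.
4. Handle missing OI, blood gas or echocardiogram data endpoint by endpoint, by one written rule for both groups, and report the number available per group.
5. Report any control rejected after selection, with the reason.

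The cost is a few sentences and settling the control list before abstraction. No new patients or data are needed. The downside is that some endpoints may have fewer than 20 controls with data.

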#### 3.1.1 Screening Phase

Potential subjects will be screened on an antenatal basis in the CHOP Center for Fetal Diagnosis and Treatment (CFDT) and the SDU. We will identify and screen all women carrying a fetus at least 32 weeks gestation with a prenatal diagnosis of

---

CDH who plan to deliver in the CHP SDU. We will approach the parents during a prenatal visit at the CFDT or on an antenatal inpatient basis in the SDU to offer study participation and obtain informed consent. Given that the subjects are neonates, we will not obtain assent.

For fetuses with parental consent, we will then review the eligibility criteria again prior to and during delivery. Subjects with signed antenatal informed consent who meet all eligibility criteria will be allocated to the trial intervention at the time of birth.

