### **3.4.2 Exclusion Criteria**

1. Multiple gestation
2. Major anomalies or aneuploidy
3. Enrolled in FETO (fetal endoluminal tracheal occlusion) trial
4. Palliative care planned or considered
5. Maternal diagnosis placenta previa, accreta, or abruption
6. Maternal diagnosis pre-eclampsia requiring Magnesium sulfate therapy at time of delivery
7. OB or Neonatal provider concerns for the clinical care of the mother or infant, or study team not available.

The inclusion and exclusion criteria are the same for the interventional arm and the historical controls. Subjects that do not meet all of the enrollment criteria may not be enrolled. Any violations of these criteria must be reported in accordance with IRB Policies and Procedures.

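### Section 5.9.3 sets no reference time for applying exclusions 2 and 4 to historical controls, while DING eligibility is fixed at birth; control mortality could be understated

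*Combined protocol and SAP*

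**What the plan says.** **DING infants.** Section 3.1.1 states that, once parents have consented, "we will then review the eligibility criteria again prior to and during delivery". Section 5.9.2 then adopts intention to treat and closes the question at delivery: "All infants who meet all eligibility criteria at the time of birth and are allocated to the intervention are considered evaluable". No later check is described, so an anomaly found afterwards or a later change in the goals of care does not remove a DING infant.

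**Historical controls.** Section 5.9.3 takes the most recent registry infant matched on gestational age and CDH severity markers, and adds: "Matched historical controls will be considered evaluable if they meet all inclusion and exclusion criteria", with the further condition that the record is complete. It gives no reference time. Section 4.2.2 describes the data source: "Medical record review will include the specified secondary clinical outcomes for control infants". Outcomes are therefore already on file when controls are chosen, and nothing asks for selection without sight of them.

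**The criteria.** Section 3.4.2 lists exclusion 2 as "Major anomalies or aneuploidy" and exclusion 4 as "Palliative care planned or considered", both undated. The Abstract and Synopsis do not date them either. Exclusion 6, by contrast, is dated: "Maternal diagnosis pre-eclampsia requiring Magnesium sulfate therapy at time of delivery". Gestational age in section 3.4.1 is likewise tied to birth. The Synopsis and section 3.4.2 both say that one set of criteria serves both groups.

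**The concern.** The same words select different infants if they are read at different times. Most of the criteria are settled by delivery. Exclusions 2 and 4 are not: a genetic or cardiac diagnosis can come after birth, and palliation can first be raised during the stay.

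Exclusion 4 matters more. If it is read over the whole hospital stay, it comes close to selecting on the outcome, because palliative discussions can be expected mainly in infants who are dying. A control removed in this way is replaced by the next most recent match, so deaths would tend to drop out of the control group with no counterpart in the DING group.

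In-hospital mortality is a secondary endpoint compared between groups (sections 5.7 and 5.9.3). Section 5.10 expects no statistically significant differences and says that the secondary comparison is to supply estimates for designing a later randomized trial. The point estimates are therefore the product of this comparison. A control mortality that is too low would make DING look worse than it is, or hide a benefit.

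**Working it through.** The plan states no figure on this point, so there is none to reproduce. The check has two parts.

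**1. The text, applied to two infants with the same course**

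| Event | DING infant | Control, 5.9.3 read literally |
|---|---|---|
| Anomaly or aneuploidy first found after birth | Stays in: eligible at birth (5.9.2) | Can be judged to meet exclusion 2 and be skipped |
| Palliation first considered after birth | Stays in: eligible at birth (5.9.2) | Can be judged to meet exclusion 4 and be skipped |

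**2. Illustration of size for mortality**

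Inputs:
- m = 0.29, the CDH mortality given in section 1.1. It is a figure for CDH in general. That it applies to infants of at least 36 weeks who meet this trial's criteria is an assumption.
- 20 controls (section 3.3.2).
- f, the share of control deaths removed because of a postnatal finding or discussion. The documents give no value; 0.10 to 0.50 is an assumed range.

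If only deaths are removed and replacements come from the remaining pool, observed control mortality is m' = m(1 − f) / (1 − m·f).

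- f = 0.10: 0.261 / 0.971 = 0.269
- f = 0.25: 0.2175 / 0.9275 = 0.235
- f = 0.50: 0.145 / 0.855 = 0.170

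| f | Control mortality | Expected deaths in 20 | Apparent DING excess with no true effect |
|---|---|---|---|
| 0 | 29.0% | 5.8 | 0 |
| 0.10 | 26.9% | 5.4 | 2.1 points |
| 0.25 | 23.5% | 4.7 | 5.5 points |
| 0.50 | 17.0% | 3.4 | 12.0 points |

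In whole infants, suppose 6 of 20 die in each group. Replacing one, two or three dead controls by survivors gives 5, 4 or 3 of 20 against 6 of 20. Each replacement moves the difference by 1/20 = 5 points. Fisher's exact p is 1.00, 0.72 and 0.45, so the test would not reveal the distortion.

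**Offset from removed survivors.** Exclusion 2 read late would also remove some survivors. If a share g of survivors is removed, m' = m(1 − f) / [m(1 − f) + (1 − m)(1 − g)]. With g = f the bias is zero. With f = 0.25 and g = 0.10 (both assumed), m' = 0.2175 / (0.2175 + 0.639) = 0.254 rather than 0.235. The net bias therefore depends on how far f exceeds g.

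**Scale against chance.** The binomial standard deviation of deaths among 20 controls is √(20 × 0.29 × 0.71) = 2.0. The expected shifts are 5.8 − 5.4 = 0.4, 5.8 − 4.7 = 1.1 and 5.8 − 3.4 = 2.4 deaths.

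**The case against.** The strongest reply is that these are delivery-room entry criteria. Several are tied to birth or delivery, the document says twice that they are the same for both groups, and a sensible abstractor would carry the at-birth rule of 5.9.2 over to controls. This has force. A reader might infer that controls are in fact judged on their completed records under a different rule, and the documents do not support that: no section tells anyone to use postnatal information for control eligibility. What remains is that nothing rules it out, the two criteria most open to it are undated, and the outcomes are on file when the choice is made.

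A second reply is matching. A reader might infer that control severity would also be understated. Any replacement must match the same DING infant on gestational age and CDH severity markers, which limits such a shift. Matching does not undo selection on death among infants of similar antenatal severity, so the mortality concern stands. An effect on ECMO is possible, but nothing here quantifies it.

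A third reply is that little depends on this. The primary endpoint uses DING infants only and is untouched. The comparison is exploratory, already imprecise at 20 per group, and not randomized. The bias described under exclusion 4 works against DING and would not manufacture a benefit. All of that is correct and limits the weight of the point. It does not remove it, because section 5.10 names these estimates as inputs to the next trial.

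**Conclusion.** The gap in the text is real: eligibility has a reference time for DING infants and none for controls, and exclusions 2 and 4 can change status after birth. That the gap would be used to drop controls is an inference, so this is an ambiguity that permits bias and not a demonstrated difference in treatment of the groups.

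If exclusion 4 were read over the whole stay, control mortality would probably be understated. The illustration gives 27%, 23% or 17% in place of 29%. It rests on the background mortality applying to this population, on an f that the documents do not give, and on few survivors being removed. Late use of exclusion 2 would partly offset it. The effect is confined to the secondary comparison, chiefly mortality, and to the planning estimates drawn from it. The point deserves correction because the remedy is cheap and makes the statement of identical criteria true in practice.

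A reader might also infer that every exclusion should be judged in both groups on antenatal information alone. That would conflict with the review during delivery in section 3.1.1, the at-birth rule in 5.9.2, and exclusions 5 to 7, which can turn on events during delivery.

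**What to change.** In section 5.9.3, state that exclusions 2 and 4 are applied to historical controls only on information documented up to the time of birth, in line with 5.9.2, and that later diagnoses or care decisions do not remove a control.

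Select controls from the eligibility and matching data available at birth, including gestational age at birth, by someone without sight of outcomes. The check that a record is complete may require opening the outcome fields, so do it afterwards or give it to another person. Log each skipped candidate with the reason and the date of the information relied on.

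Leave the DING eligibility review prior to and during delivery, and exclusions 5 to 7, as they are.

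The cost is a few sentences, a separated selection step and a short log. The downside is that a few controls with late-diagnosed anomalies stay in, which adds some heterogeneity; DING infants with such diagnoses already stay in under 5.9.2.
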